**Version 1.4**

**25 July 2018**

### **List of Acronyms**

ART	Anti-retroviral therapy
CHW	Community health worker
EDC	Electronic data capture
FGDs	Focus Group Discussions
HIV	Human immunodeficiency virus
HIVST	HIV self-testing
HTS	HIV testing services
ID	Identity
IDIs	In-depth Interviews
LSHTM	London School of Hygiene and Tropical Medicine
PITC	Provider-initiated counselling and testing
PMTCT	Prevention of mother-to-child transmission
PopART	Population effects of Antiretroviral Therapy to reduce HIV transmission
PRA	Participatory Rapid Appraisal
SOP	Standard operating procedures
STAR	Self-testing for HIV in Africa
UNAIDS	Joint United Nations Programme on HIV/AIDS
UNZA BREC	University of Zambia Biomedical Research Ethics Committee
VMMC	Voluntary medical male circumcision

## **Summary**

---

To end the HIV epidemic by 2030, strategies are needed to reach undiagnosed HIV-positive individuals with treatment services and link HIV-negative individuals to available prevention services, including voluntary medical male circumcision (VMMC) and oral pre-exposure prophylaxis [1]. In Eastern and Southern Africa, the region with 50% of the burden of HIV, progress has been made in reaching the UNAIDS 90-90-90 targets, yet one-quarter of individuals living with HIV remain unaware of their HIV status [2]. Over the past decade, HIV testing services have evolved rapidly, from primarily facility-based service delivery to the widespread availability of community-based HIV testing strategies. These strategies have contributed to achieving the first 90 in many countries of the region, but there remain gaps in reaching men and younger people with HIV testing services.

HIV self-testing (HIVST) is a novel strategy to deliver HIV testing services that has the potential to fill the gap in the first 90 [2]. By virtue of providing more autonomy, flexibility and privacy about when and where to test for HIV, HIVST may reach the “hardest-to-reach” individuals. Since 2016, the World Health Organization has supported the implementation of evidenced-based strategies to deliver HIVST [2, 3]. HIVST is being included as part of the national HIV strategies and policies in a number of countries in the region [2]. In Zambia, where an estimated 66% of HIV-positive individuals are aware of their HIV status, [2] a trial of the door-to-door offer of HIVST as an option for how to test for HIV showed that the strategy can reach men and individuals previously not reached through an offer of home-based finger-prick HIV testing [4]. To support the development of HIVST guidelines, additional research is needed to understand how to deliver HIVST in different settings and for different populations.

The purpose of this study is to conduct an in-depth evaluation of the process of distributing HIVST through five models of HIVST distribution. The study aims to understand user and provider experiences of HIVST distribution, contextual factors that affect HIVST distribution, to measure the cost of distribution, and determine who is reached if the distribution model is to deliver an HIVST to an index individual for distribution to their partner (termed secondary distribution of HIVST). The HIVST distribution models that will be included in this case study include: VMMC clinics, public health facilities, community-led distribution through community structures such as small shops, and secondary distribution of HIVST through antenatal care (ANC) and HIV testing and treatment services.

The specific objectives of the study, for all models of distribution, are to:

1. Describe, quantitatively, the process of distributing HIVST kits through each of the five distribution models;
2. Understand individuals' experiences of the different models of HIVST distribution;
3. Explore contextual factors likely to influence the implementation and acceptability of different models of HIVST distribution;
4. Evaluate the frequency and nature of social harms associated with distribution of HIVST kits;

5. Develop generalizable qualitative tools that can be used to evaluate different distribution models among key target populations;
6. Costs, from the patient and the provider-perspective, for providing and accessing HIVST kits;
7. The incremental cost-effectiveness of additional HIVST distribution models, and
8. Patient costs and their willingness-to-pay for HIVST models

To meet these objectives, the study will combine qualitative and quantitative data collection.

To measure the process of HIVST distribution, routinely collected programme data will be used to describe the number of HIVST kits distributed through each of the five distribution models. Qualitative data collection will complement quantitative data by providing insights into users and providers experiences (objective 2), and contextual factors that influenced distribution of HIVST through each of the five models (objective 3). Qualitative data collection methods will include focus group discussions (FGD), in-depth interviews (IDI), community consultations, physical and social mapping, observations and stakeholder discussions. These methods will also be used to document the emergence and management of social harms.

Economic evaluation methods will include document reviews and exit interviews with individuals accessing HIV testing services.

In the **two secondary distribution models**, the study will explore factors associated with successful secondary distribution of test kits. Specific objectives are to measure:

9. Factors associated with acceptance of HIVST for secondary distribution to index patients, acceptance being evidenced by accepting an HIVST kit(s) for onward secondary distribution.
10. Factors associated with the successful secondary distribution of HIVST to the sexual partners (the intended users of the secondary distribution HIVST kits) of index patients, as evidenced by the proportion of index patients who report that their primary partners used the HIVST kit within 1 month of distribution
11. The proportion of intended users of the secondary distribution HIVST kit who report having accessed confirmatory testing, or HIV prevention or care services within 3 months of distribution
12. User experiences and factors affecting the potential for social harms

To meet these objectives, we will administer a quantitative exit interview after the clinical consultation to determine the proportion of individuals who accepted an offer of an HIVST for secondary distribution and factors associated with acceptability of an offer of a secondary distribution HIVST (objective 9). For individuals who accepted the offer of a secondary distribution HIVST, we will conduct a follow-up questionnaire approximately 1-month after the initial exit interview to measure use of the HIVST kit (objective 10) and will follow-up their partner approximately 3-months after distribution to measure linkage to confirmatory testing, HIV care or prevention services (objective 11). To complement the quantitative data, a purposive sample of individuals participating in the exit interview will be followed-up at three-time points as part of a qualitative cohort, with IDI conducted each time point to understand

user experiences, factors influencing secondary distribution of an HIVST, and social harms (objective 12).

## **1. Background and Purpose of the Study**

---

### **1.1 Background and rationale**

Over the past decade, the delivery of HIV testing services (HTS) across southern Africa has evolved from solely facility-based to delivery of HTS through community-based settings, including community-based campaigns, mobile vans, and the door-to-door offer of home-based HIV testing from lay counsellors.[5] In many sub-Saharan African countries, this scale-up of HTS has led to an increase in the proportion of individuals ever-testing for HIV and receiving the result of an HIV test, and has contributed to progress in reaching the first-90 of the UNAIDS 90-90-90 targets.[6-9] In 2016 in eastern and southern Africa, an estimated 76% of individuals living with HIV knew their HIV-positive status, among whom 79% were on anti-retroviral therapy (ART) treatment.[2, 8] In 2016 in Zambia, 70% of women and 63% of men knew their HIV-positive status.[10] A similar percentage (~85%) of men and women who knew their HIV-positive status self-reported ART treatment use.[10] Relative to 2010, there was a 4% decline in HIV incidence in 2015 in eastern and southern Africa.[11]

Despite progress in the region towards the UNAIDS 90-90-90 targets, HIV incidence remains high among a number of sub-populations and there are critical gaps along the treatment cascade, with a third of individuals living with HIV remaining undiagnosed.[2, 8] To improve all steps in the HIV care continuum and link more people into HIV prevention services, including voluntary medical male circumcision (VMMC) and oral pre-exposure prophylaxis (PrEP), there remains a need to improve access to HTS in order to facilitate linkage to HIV prevention, or treatment and care services.[11] Among the populations hardest to reach with HTS are men, adolescents and younger adults, and populations with higher levels of mobility.

### **1.2 HIVST as a strategy to increase uptake of HIV testing services**

Self-testing for HIV (HIVST) is an approach to delivering HTS that provides greater confidentiality and autonomy about where and when to test.[12] Studies have shown that HIVST is feasible, acceptable, can achieve a high level of accuracy with lay counsellor support for use,[4] and can reach partners of women attending health facilities.[13] Studies of secondary distribution of HIVST to the partners of women attending ANC or post-partum services and to female sex workers in Kenya have shown high reported use of HIVST by primary sexual partners.[14]

### **1.3 Regulatory developments relating to HIVST and their ethical considerations**

Since 2016, the WHO endorsed HIVST as an additional approach to delivering HIV testing services (strong recommendation, moderate quality evidence) [3]. The recommendation, however, acknowledged the need for additional research on best practice for delivering HIVST services in different settings and for different populations [3]. In addition, the HIVST kit being used for implementation of the STAR (Self-testing for HIV in Africa) studies (an oral fluid, or mouth swab, test: OraQuick HIVST kit) was pre-qualified by WHO as suitable for use in low- and middle- income countries, based in part on clinical performance data provided by Zambart

in Zambia [4]. The OraQuick test is currently the only product with WHO pre-qualification for HIVST and has been approved for routine use in Zambia, with a country operational framework under development by the Zambian HIVST Technical Working Group. As such, OraQuick packaged for HIVST is no longer an investigational product, and promotion of HIVST with this product does not in itself require ethical approval.

#### **1.4 Studies of HIVST distribution in Zambia**

In addition to clinical performance studies, three cluster-randomised trials of community-based distribution have been conducted in Zambia. In one trial, conducted in four urban communities, we found that the door-to-door offer of HIVST as an option for HIV testing by lay counsellors, which included the option for individuals to take an HIVST for secondary distribution, reached men and younger adults.[15] The second trial, a cluster randomised trial of community-based distribution of HIVST is ongoing as part of STAR Phase I. A third trial among female sex workers, using peer educators and their clients as the unit of randomization, found that HIVST was acceptable, but did not address gaps in the care cascade among a population with high levels of HIV testing and linkage to care overall [16]. Findings arising from the completed HIVST trials, and other studies of HIVST in the region, have led to HIVST being adopted as a routine service delivery through health facilities in Zambia.

There remains, however, a need to understand the relative costs, benefits and harms associated with different models of delivery; whether different models of HIVST distribution are feasible, reach individuals, particularly men, previously unaware of their HIV status; and link individuals to HIV prevention or care services. In particular, there is a need for evidence of less labour-intensive and costly models of HIVST distribution. Numerous models of HISVT distribution are being tried in different settings. How these models are implemented in practice, how different models of distribution are experienced by intended users, and whether these models reach population subgroups underserved by available HTS all need to be understood to support decision-making around resource allocation for HIVST.

The starting point of the current study is, therefore, to use mixed-methods case studies to evaluate the costs and effects of five models of distribution on societal perspectives of HIV and testing for HIV. We will also evaluate the health worker perceptions of HIVST as a potential addition, but also a potential threat, to their delivery of HIV services. This collection of case studies will provide quantitative and qualitative evidence of the process of delivering HIVST services, understand who is reached through these models of HIVST distribution, particularly secondary distribution, and the experiences of individuals reached through these models.

#### **1.5 Study Purpose**

The purpose of this observational research study is to evaluate the process of delivering HIVST services through five promising models of HIVST distribution (Table 1). In this study, we will use a case study approach, combining qualitative, economic and quantitative data collection methods, to describe the process of distributing HIVST through each model, provide in-depth understanding of user and provider perspectives of each model, and the experiences of individuals accessing HIVST services. For models 4 and 5 (secondary distribution models), we

will recruit cohorts of individuals to evaluate how best to target secondary distribution of HIVST kit, to maximise uptake and linkage to confirmatory testing, HIV prevention and care services.

Across all models, we will develop approaches for anticipating, documenting and mitigating social harms, although these have proved to be rare in other HIVST distribution models [17, 18].

**Table 1: Summary of HIVST distribution models**

Model	Description	Implementer
1 VMMC	VMMC mobilizers distribute HIVST to men interested in VMMC.	SFH
2 Facility-led and Community-led	The facility-led model will utilize existing clinics to distribute HIVST kits within specified departments of the facility and during outreach programs.  HIVST kits will be distributed using existing community structures such as shops of hubs (kanterbas) that are otherwise not directly linked to the health facilities. Communities will determine the best way to distribute the tests and manage all distribution activities.	SFH Zambart and MOH  SFH and Zambart
3 Workplace	Distribution of HIVST in targeted workplaces where HIV risk may be high (uniform/security professionals, truck drivers, taxi ranks etc.) and testing using routine finger-prick test is low or unsuccessful, HIVST distribution through peer educators or distribution agents.  Distribution will be done in a private room or outside in a tent. Workers will walk in at their own time to collect an HIVST. Process data will be collected using a self-administered questionnaire. There will be no individual tracking for linkage to care and treatment.	SFH
4 Secondary Distribution through ANC	This model is part of the facility-led HIVST distribution model, above. HIVST for secondary distribution will be offered to women attending ANC for their primary partners.	SFH and MOH
5 Secondary distribution through individuals who know their HIV	Trained lay counsellors for Zambart models and SFH and MOH staff for models implemented by SFH will distribute HIVST through individual HIV+ patients. The lay counsellors will offer HIVST kits to HIV positive individuals who self-report to: be in a discordant	Zambart, MOH and SFH

---

positive status	relationship; to have a partner with unknown HIV positive status or to have HIV negative partner who wishes to re-test.
-----------------	---

---

## **2. Study aim and objectives**

---

### **2.1 Study aim**

The overall aim of this study is to inform early scale-up and guideline development for approaches to distributing HIVST in Zambia through in-depth evaluation of five promising distribution models. The evaluation will use a mixed method approach using qualitative, economic and quantitative data.

The qualitative analysis will explore user and provider perspectives and experiences, and the contextual factors that affect the acceptability of HIVST and subsequent post-test services where HIVST are distributed through different approaches. Data on social harms and risk factors for social harms will also be explored.

The quantitative components of this study will include using routinely collected programmatic data to describe the process of HIVST distribution and, in the two secondary distribution models, recruitment of larger cohorts of index patients (attending ANC and HIV testing and treatment services). The cohorts will investigate who is reached through secondary distribution and evaluate the factors associated with a successful secondary distribution. The cohorts will allow us to measure the proportion of HIVST kit recipients who link to confirmatory testing, prevention or care services. Accuracy of secondary distribution HIVST kits will not be evaluated here but is being included in a parallel STAR study in Malawi.

The economic analysis will involve programmed expenditure review, complemented by field observations, to calculate the health systems costs. Field observations help in generating allocation factors across activities and shared resources as well as identifying associated economic costs of distributing HIVST. We also conduct interviews with testers, including potential testers, to assess patient's costs of accessing HIV services as well as their willingness to pay for HIVST. We also conduct interviews with distributors, for community-led models, to assess their willingness to accept distribution of the kits.

### **2.2 Study objectives**

For each of the five distribution models, the specific objectives are to use routinely collect programmatic data and qualitative data from the case studies to:

1. Describe, quantitatively, the process of distributing HIVST kits through each of the five distribution models;
2. Understand individuals' experiences of the different models of HIVST distribution;
3. Explore contextual factors likely to influence the acceptability of different models of HIVST to direct and secondary-distribution kit recipients. For example, at community level we will explore how availability of alternative HTS, anticipated and enacted stigma, and location of the distribution models influence people's choices. At interpersonal level, we will explore how power dynamics within a couple influence individuals' decisions.

4. Evaluate the frequency and nature of social harms associated with distribution of HIVST kits, and
5. Develop generalizable qualitative tools that can be used to evaluate different distribution models among key target populations

For four of the five models (all models except VMMC) we will also measure:

6. Costs, from the patient and the provider-perspective, of accessing and delivering HIVST kits, and those relating to linkage into confirmatory testing and care for individuals who self-test HIV-positive
7. The incremental cost-effectiveness of additional HIVST distribution models
8. Patient costs and their willingness-to-pay for HIVST

For the two secondary distribution models (implemented in ANC and HIV testing and treatment services), we will recruit a cohort (Secondary Distribution cohort) of index patients and their sexual partners (intended users of the HIVST kit) in order to investigate:

9. Factors associated with acceptance of HIVST for secondary distribution to index patients, with acceptance evidenced by accepting an HIVST kit(s) for onward secondary distribution.
10. Factors associated with the successful secondary distribution of HIVST to the sexual partners (the intended users of the secondary distribution HIVST kits) of index patients, as evidenced by the proportion of index patients who report that their primary partners used the HIVST kit within approximately 1-month of distribution
11. The proportion of intended users of the secondary distribution HIVST kit who report having accessed confirmatory testing, or HIV prevention or care services within approximately 3-months of distribution
12. User experiences and factors affecting the potential for social harms

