### **4.3. Quantitative methods**

#### **4.3.1 Process data**

Process data collected during distribution of HIVST kits by the SFH and Zambart distributors will be used. SFH has developed simple tools (Appendix 2) that distributors will use for all the distribution models. The information to be collected include age, sex, level of education, occupation, whether an individual accepts the test kit or not and the reasons for not accepting the test kit. In all the distribution models, this information will be collected using a simple paper-based questionnaire or register. The process measures collected for each of the five distribution models will include:

[figure not shown]
- 1) The number of HIVST kits offered through the five models of distribution, the number of HIVST kits accepted and the number of HIVST kits returned.
- 2) Proportion of individuals offered an HIVST who accept the offer, by model of distribution

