### **7.3 Quantitative secondary distribution cohort data**

For the quantitative data arising from the secondary distribution cohorts, we will conduct analyses separately for the ANC and HIV testing and treatment cohorts. We will use descriptive analyses to describe the proportion of individuals accepting an offer of HIVST and the proportion who report that their partner used the HIVST. We will use standard logistic regression adjusting for study site to explore factors associated with accepting an offer of HIVST and with reported use of the HIVST.

Although the index individuals will be asked about linkage to care at 1-month follow-up, we will measure linkage to care using data from the intended users followed-up within 3-months after distribution. Linkage will be measured as the number of individuals reported to have linked to care (defined as accessing confirmatory testing services or attending an HIV care clinic for HIV-positive individuals or accessing VMMC services for HIV-negative males) among those who reported use of the HIVST.

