### **8.4 Privacy and Harm Reduction**

All efforts will be made to ensure that participants are provided with privacy when answering questions which may be sensitive. The research assistants will be trained to work with the participant to ensure a safe and private space is available, either in the participants' home, the facility or if this is not possible in another place of the participants' choice.

Some questions, such as those about violence and social harms are especially sensitive and will require special training of the research assistants. Research assistants will be equipped with information about access to services available in the communities for individuals experiencing violence and social harms, and will be trained to refer and support any participants who have experienced violence. The questions about violence and also about relationships and power within relationships are critical to the understanding of the safety and applicability of secondary distribution of HIV test kits and so are asked for this purpose only. All participants will be reminded that they can decline answering any questions at any time.

A social harm reporting system will be maintained in research areas and will be based on earlier social harms reporting systems developed by Zambart and SFH for the PopART trial and STAR. Potential social harms will be evaluated for seriousness, and likely relatedness to HIVST by the study PI. Social harms reporting, and investigation will take into account confidentiality and anonymity. Tracking of social harms will then enable SFH/Zambart to assess and mitigate adverse events arising from HIVST.

All social harms are reported to the STAR Initiative's independent Technical Advisory Group. Social harms related to HIVST will also be reported to the ethics committees.

The Standard Level of Serious Adverse Event will be used [25] for reporting the following serious adverse events to study leadership within two working days of becoming aware of the event:

- 1 Death;
- 2 Disabilities/incapacities;
- 3 Hospitalisations that are “suspected adverse drug [procedure] reactions” (cannot rule out relationship to study procedures), or
- 4 Other Grade 4 events that are “suspected adverse drug [procedure] reactions” (cannot rule out relationship to study procedures).

Annual reports with full listings of SAEs will also be submitted to Ethics Review Boards.

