SHS_Fu_2	Has anything good happened to you or in your relationship which you think was a result of you talking about HIV testing or giving the test to your partner	Yes; No; Don't know	
SHS_Fu_2a	If yes; What was good? ( tick all that are relevant)	Discussed HIV; Was able to tell my partner my HIV status; Know my partners HIV status; Felt more comfortable with my partner; Felt more able to discuss issues with my partner; My partner was more loving/caring; Resolved some of our issues in our relationship Other ( free text)	
SHS_Fu_3	From the time your partner received the HIV self-testing kit, Has your partner ever.....		
SHS_Fu_3a	Pushed, grabbed, slapped, choked, hit or kicked you?	Yes; No; Don't know	1; 2; 3
SHS_Fu_3b	Threatened to hurt you, your children or someone close to you?	Yes; No; Don't know	1; 2; 3
SHS_Fu_3c	Insulted you or made you feel bad about yourself?	Yes; No; Don't know	1; 2; 3
SHS_Fu_3d	Taken away money or resources that you/your children need to survive?	Yes; No; Don't know	1; 2; 3
SHS_Fu_3e	Threatened to divorce you?	Yes; No; Don't know	1; 2; 3

SHS_Fu_3f	Sent you back to your family home?	Yes; No; Don't know	1; 2; 3
SHS_Fu_3g	Forced you to have sex when you did not want to?	Yes; No; Don't know	1; 2; 3
SHS_Fu_4a	[If yes to any of the above GBV questions] Did this happen as a result of discussing HIV testing with your partner?	Yes; No; Don't know	1; 2; 3
SHS_Fu_4b	Do you think any of these things were the result of having offered an HIV self-test to your partner?	Yes; No; Don't know	1; 2; 3

**Follow-up questionnaire for secondary distribution cohorts – questionnaire for intended user of secondary distribution HIVST kit**

Section 0: Preparing for the survey			
Variable Name	Question	Option	Option codes
PS 1	What is the date today?	[time stamp]	
PS 1a	CLINIC NAME	[EDC CODE]	
PS 2	Scan participant barcode		
PS 3	Which community are you in?	Community 1	1
		Community 2	2
		Community 3	3
		Community 4	4
		Community 5	5
		Other	Specify
PS 4	What models of HIV self-testing distribution are in this community? [tick all that applies]	VMMC	1
		Community- or facility led	2
		Secondary distribution through ANC	3
		Secondary distribution through ARTHIV testing and treatment services	4
		Workplace	5
		Other (Specify)	6
PS 5	Through which distribution model was the client offered an HIV self-testing kit?	Secondary distribution through ANC	3
		Secondary distribution through ART	4

Section 1: Consenting Process			

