M_HIV_Test_IU 12	I wanted to be able to get treatment without delay if I tested and was HIV-positive	No; Yes	0; 1
M_HIV_Test_IU 14	I accepted as I had no reason to decline	No; Yes	0; 1
M_HIV_Test_IU 15	I accepted because my partner wanted me to test	No; Yes	0; 1
M_HIV_Test_IU 16	I accepted because my partner forced me to HIV self-test	No; Yes	0; 1
M_HIV_Test_IU 17	I accepted to test because my wife is pregnant so I wanted to protect the health of my wife and baby	No; Yes	0; 1
M_HIV_Test_IU 18	I have or I have had an HIV positive sexual partner and I wanted to know my status	No; Yes	0; 1

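### Objective 4 promises the frequency of social harms, but the sources it names cannot give a credible one, and the cohort harm items that could do so for models 4 and 5 are not linked to it

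*Protocol*

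**What the plan says.** Section 2.2 states objective 4, for each of the five models, as: "Evaluate the frequency and nature of social harms associated with distribution of HIVST kits, and". The lead-in to objectives 1 to 5 gives their sources: "the specific objectives are to use routinely collect programmatic data and qualitative data from the case studies to". The Summary, after listing the qualitative methods, adds: "These methods will also be used to document the emergence and management of social harms".

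Section 4.3.1 describes the process data: "The information to be collected include age, sex, level of education, occupation, whether an individual accepts the test kit or not and the reasons" for refusal, plus counts of kits offered, accepted and returned. Section 7.2 analyses offers, acceptance and reasons for refusal.

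For the secondary distribution cohorts, section 4.3.2 lists outcomes on acceptance, use and linkage only. Section 7.3 states its descriptive part, on acceptance of the kit and its use, as: "We will use descriptive analyses to describe the proportion of individuals accepting an offer of HIVST and the proportion who report that their partner used". It then models acceptance and use and measures linkage. The second paragraph of section 7.4 again covers use and linkage.

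The follow-up form for index patients in Appendix 3 has seven harm items (SHS_Fu_3a to 3g) and two attribution items (4a, 4b). The second attribution item is: "Do you think any of these things were the result of having offered an HIV self-test to your partner". The exit interview asks about threats, physical violence and insults over the previous 12 months (QIPV 3, 4 and 6). The intended-user form includes, among motivators of testing: "I accepted because my partner forced me to HIV self-test".

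Section 8.4 calls the questions on violence and on power in relationships "critical to the understanding of the safety and applicability of secondary distribution of HIV test kits".

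**The concern.** An objective that promises a frequency needs a defined group of people who were asked, and a count among them. None of the sources named in section 2.2 supplies both.

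The gap matters most in models 4 and 5. Section 10.2 says that giving a woman a kit for her partner may carry serious risks and that evidence on harm after secondary distribution is thinner. Yet section 5.1 excludes exactly these two models from the community mechanisms for identifying and documenting harms and turns to qualitative participants instead. Sections 8.4 and 10.2 describe a reporting system and network with no such exclusion.

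Followed as written, a statement that few or no harms occurred could inform national scale-up on the basis of a few selected interviews and spontaneous reports. Violence that predated the kit would not be separated from violence that followed it. Meanwhile, structured answers from several hundred people per cohort would have no stated role in the harm objective.

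**Working it through.** **1. What each source can supply**

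| Source | Harm item | Defined group asked |
|---|---|---|
| Process data (4.3.1, 6.2, 7.2; ART, MCH and workplace tools in Appendix 6) | None shown | Yes, people offered a kit |
| Qualitative work (4.2, 5.1) | Yes | Purposive: 46 interviews, 12 focus groups |
| Qualitative cohort | Yes | Purposive: 24 people in 4.2, 12 in 5.2 |
| Harm reporting system (8.4, 10.2, Appendix 7) | Yes | No; spontaneous reports, no rate defined |
| Index follow-up questionnaire (Appendix 3) | Seven harms, two attribution items | Yes, re-interviewed index patients |

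The columns of the facility and community register in Appendix 6 are not visible in the text available, so nothing is claimed about them. Only the last row joins a harm item to a defined group that was systematically asked. It covers models 4 and 5 only, and section 2.2 does not name it for objective 4.

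**2. Number available in the cohort**

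Section 5.4 needs about 300 per cohort after up to 30% loss: 300 / (1 − 0.30) = 428.6, so 429. The plan recruits about 450, and 450 × 0.70 = 315 per cohort, or 630 over both.

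The SHS_Fu_3 stem asks about the time since the partner received the kit, so it has meaning only where the kit was given (Use_HIVST 3 = yes). Hence 315 is a ceiling. The protocol gives no figure for the share who give the kit. Assuming 50% to 80%: 315 × 0.50 ≈ 158 and 315 × 0.80 = 252.

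**3. Precision with no events**

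The exact two-sided 95% upper limit is U = 1 − 0.025^(1/n).

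| n | Basis | U |
|---|---|---|
| 12 | qualitative cohort, section 5.2 | 26.5% |
| 24 | qualitative cohort, section 4.2 | 14.2% |
| 46 | all in-depth interviews | 7.7% |
| 158 | cohort, 50% gave the kit (assumed) | 2.3% |
| 252 | cohort, 80% gave the kit (assumed) | 1.5% |
| 315 | cohort, ceiling | 1.2% |
| 630 | both cohorts, ceiling | 0.6% |

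The first three rows treat purposive samples as random, so they are indicative only.

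**4. Chance of seeing no case at all**

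Section 10.2 quotes 3% feeling coerced in an earlier programme. Used purely as an illustration, the chance of no case is 0.97^n: 69% for n = 12, 48% for n = 24, 25% for n = 46, and below 0.01% for n = 315. If 9 of 315 reported a harm (2.9%), the exact 95% interval would be 1.3% to 5.4%.

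**The case against.** Several stronger readings are tempting, and the document does not support them.

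- *Objective 4 cannot be answered at all.* Half of it concerns the nature of harms, which interviews, focus groups and harm reports can describe. Programmatic data may also be read to include the event and social harm forms in Appendix 7, with the monthly collation in section 10.2. Reported harms over kits accepted by model would then be a crude rate. That stands, but no such rate is defined, spontaneous reports probably miss cases, and coverage of models 4 and 5 is unclear.
- *The violence questions are collected and never used.* Section 8.4 gives applicability as well as safety as their purpose. Section 4.3.2 uses history of gender-based violence as a factor for acceptability, and the exit interview ties positive answers to a safety check before a kit is given. What is missing is their use to measure harm after distribution.
- *The cohort is not linked to harms.* Section 2.2 lists objective 12, on factors affecting the potential for harms, under the cohort. But the Summary assigns that objective to the purposively sampled qualitative cohort, and it concerns factors, not frequency.
- *The missing analysis belongs in the statistical analysis plan.* A table layout does, and the absence of one is no fault. But the assignment of sources to objectives and the list of cohort outcomes are fixed in the protocol, and neither includes these items.
- *The contrast of 26.5% with 1.2% measures the loss exactly.* It does not. The protocol never proposes a rate from the qualitative cohort, binomial limits on a purposive sample are only indicative, and 315 is a ceiling. If the item applied only to the 40% to 60% whom section 5.4 assumes will report use (126 to 189 people), the zero-event limit would be 2.9% to 1.9%. Receipt should be at least as common as use, so this is pessimistic, and the ordering is unchanged.
- *The partner item gives a clean coercion rate.* Under section 5.2, partners are approached only if the index patient reports use and gives permission. Someone who coerced a partner can withhold it.

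**Conclusion.** The concern holds for frequency, not for nature. The sources named in section 2.2 cannot give a credible frequency of social harms: the process data shown have no harm item, the interviews are few and purposive, and the reporting system has no rate defined. Section 5.1 must be reconciled with sections 8.4 and 10.2 on whether harm reporting covers models 4 and 5.

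For those two models the data needed are already being collected and would bound a harm not seen at all at about 1.2% per cohort at best, or roughly 1.5% to 2.3% under the assumed 50% to 80% handing over the kit. This rests on the planned 450 recruits and 30% loss, and on harms being no more common among those lost. For models 1 to 3 nothing in the protocol gives more than passive reports. This should be corrected. It does not threaten the primary outcome.

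**What to change.** - **Section 2.2 and Summary:** name the 1-month index questionnaire as the source for the frequency of harms in models 4 and 5. Keep the qualitative data for their nature. Label any frequency for models 1 to 3 as passive reports, expressed as reported harms per kit distributed.
- **Sections 4.3.2 and 7.3:** add one descriptive secondary outcome per cohort: the proportion reporting any SHS_Fu_3 item, and the proportion attributing it to the test discussion or the kit (4a, 4b), with exact 95% intervals. The denominator is re-interviewed index patients with Use_HIVST 3 = yes; also show the number who did not give the kit.
- **Baseline split:** divide threats, physical violence and insults by QIPV 3, 4 and 6, noting that the baseline recall period is 12 months. Show baseline QIPV for those lost to follow-up.
- **Forced testing:** report M_HIV_Test_IU 16 as coercion to self-test, which the protocol's own grading table lists as a harm. State that interviewed partners are reached only through index-reported use and index permission, so the figure is probably a lower bound.
- **Reconcile** section 5.1 with sections 8.4 and 10.2 on coverage of models 4 and 5, and sections 4.2 and 5.2 on the size of the qualitative cohort.

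The cost is protocol wording and one descriptive table per cohort from items already in the forms. No new participants or data are needed. Some reported harms will be violence that was already present, which the baseline split makes visible.
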